**1 LIST OF ABBREVIATIONS**

AE	Adverse Event
CRF	Case Report Form
CV	Curriculum Vitae
EC	Ethic Committee
ENT	Ear Nose and Throat
ID	Identification
AE	Adverse Event
SAE	Serious Adverse Event
SOP	Standard Operating Procedures
RS	Rhinosinusitis
CRS	Chronic Rhinosinusitis
FESS	Functional Endoscopic Sinus Surgery
BSD	Balloon Sinus Dilation
EC	Ethics Committee
IRB	Institutional Review Board

## 2 SYNOPSIS

Protocol Number	SD-001
Protocol Title	Safety and Effectiveness Evaluation of the Sinusway™ Device for Endoscopy of the Nasal Cavity and Paranasal Sinuses in Conjunction with Sinus Balloon Dilation
Participating Countries	USA
Clinical Phase	Open, multi - center, prospective, feasibility study
Investigational Study Device	Sinusway™, a flexible, steerable endoscope, by 3NT Medical Ltd.
Study Procedures	Up to 15 Patients scheduled for sinus balloon dilation will be examined with Sinusway™ before and as part of balloon sinus dilation in the operation room (OR) or office setting (Office). The patients will attend the following: 1. Visit 1: Screening and Enrollment, as part of pre-operative visit 2. Visit 2: Sinusway evaluation at the time of the procedure
Study Population	15 adult patients, male or female, scheduled for Sinus Balloon Dilation.
Study Purpose	To assess the safety and initial performance of Sinusway™ in patients in terms of access and visualization of the nasal anatomy and paranasal sinuses, usability (alone and in conjunction with balloon dilation instruments), visualization quality, and irrigation.
Study Endpoints	
Primary – Safety Endpoints:
 
 
• Device related adverse events
 
 
Secondary – Performance Endpoints:
 
 
• To evaluate the ability to access and visualize the nasal anatomy including the maxillary, frontal, and sphenoid sinuses.
 
• To evaluate usability by filling a user questionnaire
 
• To evaluate irrigation of the nasal anatomy
 

Inclusion/Exclusion Criteria	
Inclusion Criteria:
 
 
1. Male or female patient indicated for balloon sinus dilation procedure by the ENT specialist
 
2. Patient age: adult (>18 years old)
 
3. Patients in general good health in the opinion of the investigator as determined by medical history and physical examination
 

	
4. A patient who is able to understand the requirements of the study, is willing to comply with its instructions and schedules, and agrees to sign the informed consent
 
Exclusion Criteria:
 
 
1. Known history of any significant medical disorder, which in the investigator's judgment contraindicates the patient's participation
 
2. Patients with known current or previous bleeding disorder receiving anticoagulants (e.g., chronic Coumadin treatment)
 

Study Duration	
Per Patient: between 1 day and 30 days, depending on the interval between pre-operative visit (inclusion) and day of procedure.
 
Total 10 months to recruit and treat 15 patients.

Statistical Analysis Plan	NA

## 3 BACKGROUND

### 3.1 Nasal Endoscopy

The paranasal sinuses are 4 pairs of air-filled bony spaces that surround the nasal cavity and are lined with mucous membrane densely covered with cilia that facilitates mucociliary clearance and drainage into the nasal cavity. Infection of sinuses, or rhinosinusitis (RS), is caused when mucociliary functionality is compromised and/or the sinus ostia is compromised causing the sinuses to become congested and eventually blocked. RS is a severely debilitating quality of life condition, which is characterized by throbbing headaches and facial pressure, purulent nasal discharge, and nasal obstruction. Chronic rhinosinusitis (CRS) is a chronic disease that involves long-term inflammation of the nasal and paranasal sinus mucosa with a minimum duration of 12 weeks. CRS causes not only physical suffering, but also impacts psychological wellbeing and daily functioning. CRS is an extremely common condition, affecting 29.2 million (14.2%) US adults.

Nasal endoscopy is the most important diagnostic tool currently available to otolaryngologists to diagnose sino-nasal disorders [1]. Current endoscopes perform well at allowing otolaryngologists to evaluate the nasal cavity. When anatomy is favorable, endoscopes also visualize regions externally adjacent to the sinus ostia, but do not allow visualization, culture, or lavage of the sinus cavity without extensive prior surgical opening.

The endpoints of nasal endoscopy include the ability to diagnose the patient's condition and obtain a nasal culture that has some correlation with the sinus cavity contents [2]. The limitations include the inability to steer into or around narrow anatomy, to obtain an intra-sinus culture, and to visualize the sinus cavity.

A CT scan is required when diagnosing chronic sino-nasal disorders like CRS. A CT scan provides information as to whether the sinus is clear or opacified, but is often limited in providing information as to what is opacifying the sinus cavity [3]. Most importantly, CT scan is associated with radiation exposure harmful to the patient and should be avoided if possible.

Sinusway, a flexible, steerable endoscope, overcomes current technological limitations by providing sinus visualization, and irrigation. Sinusway does not pose any risk additional to the minor risks already associated with current sino-nasal endoscopy; furthermore, the risks of bleeding, pain are reduced due to the flexibility and small profile of the device which minimizes contact with the anatomy. The risk of infection is eliminated as the intra-nasal component of the device is a one-time single use disposable and does not require re-sterilization between patients.

## 3.2 Functional Endoscopic Sinus Surgery (FESS) and Balloon Sinus Dilation (BSD)

The objective of FESS is to open the natural pathways to the sinuses. Once an improved drainage system is achieved, the diseased sinus mucosa has an opportunity to return to normal. FESS involves the insertion of endoscope into the nose for a direct visual examination of the openings into the sinuses. Diseased or obstructive sinus tissue may be removed resulting in improved natural sinus drainage.

There are several sinus surgery options that can be performed in a hospital operating room or doctor's office. Balloon sinus dilation (BSD) is a minimally invasive surgery that can be performed in both settings. A small balloon is inserted into the nose; once in the right spot, it is inflated to open and drain blocked sinus pathways. The goal of balloon sinus surgery is to unblock sinus pathways and improve symptoms, reduce infections, minimize sinus headaches and restore quality of life. When performed in the doctor's office, it offers faster recovery times and may allow eligible patients to have a lower out-of-pocket cost.

## 3.3 The Sinusway Device

Sinusway, developed by 3NT Medical, is a single-use disposable handheld endoscope 2.3mm in diameter that provides a means to visualize the internal cavities of the ear, airways, nose and sinus cavities during diagnostic and therapeutic endoscope procedures.

An ENT specialist may use the device in an operating room (OR) or an office setting, for visualization and for irrigation at anatomic landmarks, including the sinuses cavities, currently inaccessible by existing endoscopes without significant surgical resection of bone and tissue.

3NT endoscopy system (See figure 1 below) includes:

1. A Multi-use handle accessory (re-processible and auto-clavable) – engages the single-use endoscope component and allows the user to mechanically control its articulation through dedicated levers. (see Figure 1, Reusable Handle)
2. A Single-use flexible endoscope (provided sterile) – includes a distal tip CMOS imager and an integrated working channel which allows irrigation through a single channel. It is the only part that comes in contact with the patient and is disposed of at the end of the procedure. (see Figure 2, Disposable Endoscope).
3. A Camera control unit (CCU) – includes a video processor and a white LED light source. The CCU includes an attachment cable which connects to the single-use endoscope, receives video images from the endoscope, and delivers LED light to the endoscope.

***Figure 1 - Reusable Handle***

***Figure 2 - Disposable Endoscope***

The Sinusway endoscope contains an articulation mechanism that supports angulation of 125° and advancement of the insertion tube over the angulated section and beyond it, effectively keeping the angulated section stationary with respect to the anatomy (See Figure 3).

*Figure 3 Angulation and advancement of the flexible endoscope*

*Figure 4 Assembled Endoscope*

When used in conjunction with a commercially available balloon dilation device, the Sinusway may facilitate minimally invasive endoscopic sinus surgery with less post-operative nasal bleeding, faster recovery time, shorter duration of prescription medication use and short term symptom improvement than traditional FESS. [4]

## 3.4 Clinical Experience with Sinusway

3NT Medical is currently conducting a clinical study in Belgium and Israel to assess the safety and initial performance of Sinusway. The study evaluates the ability of the endoscope to access and visualize the nasal anatomy and paranasal sinuses, the endoscope usability, visualization quality, and irrigation in patients undergoing FESS surgery.

The Sinusway endoscope was evaluated during eleven (11) functional endoscopic sinus surgeries (FESS) occurring in the operating room under general anesthesia. Six (6) cases were performed in two sites in Israel: Assuta M.C.(3) and Rabin M.C.(3). Five cases were performed at the University of Ghent, Belgium. Mean Subject age was 44.3 Years [23-60 yrs], 6 males, 5 females. No major technical issues were observed during the operation of the system. No adverse event reported. Device operation and physician feedback were satisfactory.

## 4 OBJECTIVES

The objective of this study is to assess the safety and initial performance of Sinusway in patients in terms of access and visualization of the nasal anatomy and paranasal sinuses, usability (alone and in conjunction with balloon dilation instruments), visualization quality, and irrigation.

For this study, up to 15 patients scheduled for sinus balloon dilation will be examined with Sinusway before and as part of balloon dilation in the operation room (OR) or office setting (Office). Additional endoscopes as available in the procedure room and as commonly used by the ENT specialist may be used.

### 4.1 Safety assessment

Safety assessment will be based upon monitoring the adverse device effects, which will be collected throughout the procedure.

All adverse events and serious adverse events will be reported in accordance with reviewing Ethics Committee /Institutional Review Board (IRB), FDA and Competent authority requirements.

### 4.2 Performance assessment

1. Ability to access the nasal anatomy and paranasal sinuses: Ability to access and visualize anatomic landmarks, including the maxillary, frontal and sphenoid sinuses, will be recorded. Successful access will be confirmed by direct visualization and transillumination where applicable.
2. Usability evaluation
3. Irrigation evaluation
4. Nasal cavity and sinuses inflammation evaluation

5. Patient pain score and tolerability, when applicable

#### **4.3 Study End Points**

##### **Primary - Safety**

All adverse device effects will be captured and summarized as defined in **Section-8**. Adverse device effects (type, frequency, severity) are expected to be similar to those reported in literature for Nasal Endoscopy (section 8).

For this study, the Safety comparison with the data of Nasal Endoscopy reported in literature will be descriptive with no statistical endpoints.

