### 8.1 Potential risks – (Sinusway):

Endoscopy is a minimally invasive, diagnostic medical procedure. Overall, nasal endoscopy is a safe and low risk procedure. Nonetheless, potential complications such as mucosal trauma and bleeding may occur, particularly in susceptible patients with increased risk of bleeding, such as those receiving aspirin or other anticoagulant medications (i.e. Plavix, Coumadin, etc.). In addition, adverse reactions to the topical decongestants or anesthetic provided prior to the procedure may occur.

Since the Sinusway endoscope will be used in conjunction with balloon sinus dilation, the following risks which are associated with BSD and/or endoscopic sinus surgery are presented.

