### Risk associated with Endoscopic Sinus Surgery

Surgeons performing routine endoscopic interventions are faced with minor complications in 5% and major complications in 0.5–1% [21]

- Infection- A patient with sinusitis is at risk of developing infection (abscesses, meningitis, etc.) Infection risk increases with the invasiveness of the intervention. The rate of intracranial infections where the intervention is maximized is 1.6% and the rate of infection-related mortality is 0.125%. It is comparable to the one of transcranial surgeries not involving the use of an endoscope [5,6,7]. The Risk of Infection following Sinusway use is mitigated since the Sinusway endoscope is a disposable intended for single use only.
- Bleeding- Bleeding may occur, particularly in susceptible patients with increased risk of bleeding, such as those receiving aspirin or other anticoagulant medications (i.e. Plavix, Coumadin, etc.) [20]. The rate of peri- or postoperative bleeding is around 2% altogether; transfusions were required in about 0.2% of cases [8,9].

- Nasomucosal injury- Nasomucosal injury may occur during transnasal endoscopy. Nasomucosal injury was assessed in 1569 patient that underwent unsedated transnasal esophagogastrroduodenoscopy (EGD), at termination of the procedure. Normal mucosa was observed in 68% of cases, redness of mucosa was observed in 19% of cases, oozing hemorrhage was observed in 12% of cases and overt bleeding was observed in 2% of cases. The hemorrhage was self-limiting and no patient required nasopharyngeal treatment [10].

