## 8.4 Unanticipated Serious Adverse Device Effect (USADE)

Serious adverse device effect which by its nature, incidence severity or outcome has not been identified in the current version of the risk analysis report.

**Anticipated:** an effect which by its nature, incidence, severity or outcome has been previously identified in the literature. For example minor bleeding.

**Please note:** All procedures carry some risk but ENT endoscopy is very safe. Minor complications are uncommon and major complications are very rare.

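### The primary count of device-related events is scored on a joint procedure/device scale, and section 4.3 points to a nasal-endoscopy frequency that section 8 gives only in words

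*Protocol*

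**What the plan says.** **Endpoint.** The synopsis gives the primary safety endpoint as "Device related adverse events". Section 8.2 defines an ADE as an adverse event related to use of the investigational device.

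**Attribution.** The relationship scale in 8.2 asks whether the *test procedure/device* caused the event, and that joint term recurs in all five grades from Definitely to Definitely not. Section 8.6 has the investigator assign relationship to the study device by the method of the preceding section, which is this scale. It also puts treatment-related and device-related events together under the ADE label.

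**Anticipated events.** Section 8.1 opens its list by saying that "the following risks which are associated with BSD and/or endoscopic sinus surgery are presented". Section 8.2 then repeats the items of that list as anticipated adverse device effects.

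**Comparator.** Section 4.3 states: "Adverse device effects (type, frequency, severity) are expected to be similar to those reported in literature for Nasal Endoscopy (section 8". It adds that the comparison with that literature is descriptive, with no statistical endpoint. On nasal endoscopy itself, 8.1 says "Overall, nasal endoscopy is a safe and low risk procedure" and names possible mucosal trauma, bleeding and reactions to topical medication. On ENT endoscopy, 8.4 says "Minor complications are uncommon and major complications are very rare".

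**The concern.** The endpoint is specific to the device, but the instrument that decides which events count is not. At Visit 2 (section 6.2) the patient has rigid endoscopy, Sinusway endoscopy, dilation with either endoscope, irrigation and a repeat Sinusway examination, under local anaesthesia with or without sedation or under general anaesthesia. The patient was already scheduled for the dilation. If its complications are counted as device effects, the primary result no longer describes the Sinusway alone. A joint score given at the visit cannot be split afterwards.

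The second problem is the reference for that count. The only comparison planned for the primary endpoint includes frequency, and the section cited for it holds no numerical frequency for nasal endoscopy. A reader of the results would have to choose a figure from another procedure. Section 6.1 says the safety information may guide device modification and later controlled studies, so both the count and its reference should be clear.

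**Working it through.** The protocol derives no rate, margin or sample size for this endpoint, so there is no figure to reproduce. The check sets the passages side by side.

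**Step 1: does the scale measure what the endpoint counts?**

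| Place | Relation named |
|---|---|
| Synopsis, primary endpoint | device |
| 8.2, ADE definition | investigational device |
| 8.2, relationship heading and all five grades | test procedure/device, jointly |
| 8.6, what the investigator assigns | study device, using the 8.2 scale |
| 8.6, what is labelled an ADE | treatment related and device related |
| 8.2, anticipated adverse device effects | items that 8.1 introduces as dilation and/or sinus-surgery risks |

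The first two rows and the first 8.6 row are device-specific. The scale and the last two rows are not. *Test procedure* is defined nowhere. Two readings follow:

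- Narrow: it means the Sinusway evaluation. A dilation injury is then scored against the Sinusway and would be graded Probably not or Definitely not.
- Broad: it means the study session, including dilation. The same injury can then be graded Probably or Definitely related, and it enters the device count.

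The general definition of adverse events in 8.2 lists procedure-related events separately from device-related ones, and there it takes procedures to mean any in the investigation plan. The protocol therefore recognises the distinction, but its scale does not keep it.

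**Step 2: size of one misplaced event.** Input: up to 15 patients (section 7), taken as 15 treated.

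- No device-related event: 0/15 = 0%.
- One dilation event counted as device related: 1/15 = 6.7%.

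With fewer than 15 treated, one event weighs more. The documents give no probability of misattribution and no dilation-specific event rate, so I put no figure on how often this would happen.

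**Step 3: what section 8 offers as a comparator for 4.3.**

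| Source in section 8 | Type | Numerical frequency |
|---|---|---|
| Nasal endoscopy (8.1) | mucosal trauma, bleeding, topical reactions | none |
| ENT endoscopy (8.4) | minor and major complications | none, words only |
| Endoscopic sinus surgery (8.1) | several | yes |
| Transnasal EGD, 1569 patients (8.1) | mucosal injury only | yes |

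For surgery, the text says surgeons are "faced with minor complications in 5% and major complications in" 0.5–1%, and "The rate of peri- or postoperative bleeding is around 2% altogether". For transnasal EGD, "oozing hemorrhage was observed in 12% of cases and overt bleeding was observed in 2% of cases", with redness in 19% and normal mucosa in 68%. Neither source is diagnostic nasal endoscopy, and section 8 does not say which one 4.3 refers to.

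**The case against.** The strongest reply is that the protocol says *device* where it matters: in the synopsis, in the ADE definition and in 8.6. The Sinusway is what section 6.1 says will be tested, whereas dilation is already indicated, so *test procedure* can fairly mean the Sinusway evaluation. *Treatment related* can mean treatment with the device, a phrase that the severity table also uses. An event with a more likely or obvious other cause is graded down. The anticipated-event list says what is foreseen and does not set causality. Separate causality fields may also exist in the case report form, which is not shown. All of this stands as a possible reading, and it is why I do not say that the count will contain dilation events. It does not remove the defect, because the narrow reading is stated nowhere and several investigators could differ on it.

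On the comparator, it is fair to say that 8.1 does supply event types, that frequency is described in words, and that the comparison is descriptive. Only a numerical frequency is missing.

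Three stronger inferences are tempting but not supported:

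- A reader might infer that section 8's bleeding figures conflict, about 2% in surgery against 12% + 2% = 14% in EGD. That sum adds mucosal oozing, graded at the end of the procedure, to one side only. The closest pair, surgical bleeding of about 2% and EGD overt bleeding of 2%, agrees.
- A reader might take the topical decongestant and anaesthetic reactions as proof that surgical risks are mixed into the device list. Section 8.1 names them under nasal endoscopy first.
- A reader might use a surgical rate to compute how likely misattribution is. That gives the chance that an event occurs, not the chance that it is put down to the wrong cause.

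**Conclusion.** The point holds in two parts and should be fixed.

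1. The device-specific primary endpoint rests on a scale that scores device and an undefined procedure together. On the broader reading, dilation events can enter the count, and each one adds 6.7 percentage points if 15 patients are treated. Confidence that the wording conflicts is high. Confidence that it would change the count is moderate, since that depends on how investigators read the term and on a case report form that is not shown.
2. Section 4.3 cites section 8 for a nasal-endoscopy frequency that section 8 gives only qualitatively.

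No error rate, sample size or decision rule is affected. What is affected is the meaning of the primary safety summary.

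**What to change.** **(a) Sections 8.2 and 8.6.** Score causality separately for (i) the Sinusway endoscope and (ii) dilation, other instruments and anaesthesia. Base the primary endpoint on item (i) and name the grades that count, stating in particular whether Possibly does, since it allows an equally likely other cause. Label each anticipated event by its source: endoscope, or dilation/surgery and medication.

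**(b) Section 4.3.** Do one of three things: name a numerical nasal-endoscopy comparator with its source; name the transnasal EGD series as a proxy for mucosal injury only, and state that limit; or delete the expectation of similarity together with the comparison.

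**Cost.** Wording changes in three sections and one or two items on the case report form, which may already hold them. No more patients are needed. Attribution within a single session remains the investigator's judgement, so the split reduces the mixing but cannot remove it. The change should be made before enrolment, because causality is judged at the visit.

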##### **Secondary - Performance**

- To evaluate the ability to access and visualize the nasal anatomy including the maxillary, frontal, and sphenoid sinuses (according to physician discretion). This ability will be verified by observing anatomic landmarks and transillumination (as Done/Not Done/Failed).
- To evaluate usability and user satisfaction- by filling a usability questionnaire regarding the device, including assessment of visualization quality. Will be completed by the user

